5.6.4. Protocol-Required Laboratory Assessments

Protocol-required laboratory parameters are listed in Table 13-1 in the protocol. The tests in this table will be performed by the local laboratory except for follicle-stimulating hormone (FSH), luteinizing hormone (LH), estradiol, progesterone, Inhibin A, Inhibin B, Anti-Mullerian hormone/Mullerian inhibiting substance (AMH/MIS), and CA-125, which will be sent to a central laboratory.

Clinical laboratory values will be expressed in international system of units (SI) units. Summaries of clinical laboratory parameters will be summarized by study visit and overall. Tables for the shift of laboratory data from baseline to the worst post-baseline value will be presented for each lab parameter. The shift from baseline to each visit will also be presented for hematology and chemistry parameters.

The actual value and change from baseline will be summarized for each visit for clinical hematology and chemistry. For analysis of tumor markers and hormones, see Section 5.5.3.

Laboratory results will also be summarized by maximum CTCAE grade as available. For lab tests with NCI – CTCAE classification, the shift from baseline to each post baseline visit and the maximum (worst) post baseline grade will be tabulated. Shift tables will summarize the count and frequency of each baseline CTCAE grade to the highest CTCAE grade on study. Laboratory tests with bi-directional grades will be presented separately for each direction (e.g., hyperglycemia and hypoglycemia). For lab tests without NCI – CTCAE classifications, the shift from baseline to each post baseline visit and the worst post-baseline value (high or low) will be summarized using the lab range indicators (normal, high, or low).

Additional shift tables will be produced for ALT, AST, alkaline phosphatase, bilirubin, phosphorus, and creatine showing shifts of below normal range, within normal range, >1 to $2 \times$ upper limit of normal range, >2 to $3 \times$ upper limit of normal range, >3 to $5 \times$ upper limit of normal range, to $> 5 \times$ upper limit of normal range from baseline to the worst (highest) post baseline value.

Box and whisker plots displaying the values over time by nominal visit will be produced for the hematology and clinical chemistry lab tests.

All laboratory results will be listed and laboratory tests with an abnormal result will be flagged. A subset listing will be presented for all grade 3 or higher laboratory values.

A summary table and a listing of participants meeting liver chemistry stopping criteria will be provided by the cycle of onset and overall. These are participants with the following conditions:

- ALT $\geq 5 \times$ ULN
- ALT $\geq 3 \times$ ULN persists for ≥ 4 weeks
- ALT $\geq 3 \times$ ULN and bilirubin $\geq 2 \times$ ULN ($> 35\%$ direct bilirubin)
- ALT $\geq 3 \times$ ULN and International normalized ratio (INR) > 1.5 , if INR measured
- ALT $\geq 3 \times$ ULN and cannot be monitored weekly for 4 weeks. Missing lab values within window will be considered not monitored.
- ALT $\geq 3 \times$ ULN associated with symptoms (new or worsening) believed to be related to liver

Serum pregnancy testing data will be presented for each participant in a data listing.

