#### **4.3. BENEFIT/RISK ASSESSMENT**

To date, the safety profile of single agent nirogacestat in participants with advanced cancer has been characterized by manageable and reversible toxicities. Currently, important identified risks related to nirogacestat include diarrhea, dermatologic reactions (maculopapular rash, hidradenitis, and folliculitis), ovarian dysfunction, electrolyte abnormalities (hypophosphatemia and hypokalaemia), and elevated liver transaminases. Important potential risks include embryofetal toxicity, effects on male fertility and in pediatric patients, epiphyseal disorder. The results of the nonclinical toxicology and safety pharmacology studies, together with the clinical experience in patients with advanced cancers, support the hypothesis that nirogacestat may represent an important therapeutic approach in patients with GCTs. Thus, the projected benefit/risk balance is considered favorable for further development in this patient population.

More detailed information about the known and expected benefits and risks and reasonably expected AEs of nirogacestat may be found in the Nirogacestat Investigator's Brochure.

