### **6.3. JUSTIFICATION FOR DOSE**

An open-label, non-randomized, Phase I dose finding study ([Messersmith et al. 2015](#)) in participants with advanced solid tumors was conducted to determine the maximum tolerated dose (MTD) and recommended phase 2 dose (RP2D) for future clinical development of nirogacestat. In the dose-finding portion of the study, the MTD of nirogacestat administered BID continuously for 21 days was established at 220 mg BID. Additional participants were subsequently enrolled in the expansion cohort at 150 mg or 220 mg BID. The RP2D in participants with advanced solid tumors was determined to be 150 mg BID by comparing the tolerability, PK, and pharmacodynamic profile of nirogacestat at these 2 doses. At a dose level of 150 mg BID, the most frequently reported AEs were diarrhea (70%), fatigue (44%), nausea (39%), decreased appetite (26%), vomiting (26%), and hypophosphatemia (22%). HES4, a target gene of Notch, measured in peripheral blood samples showed the most consistent pharmacodynamic response, with a greater than 2-fold reduction observed in 17 of 19 evaluable participants with solid tumors. Nirogacestat was also investigated as a single agent in a Phase 2 study in 19 participants with triple-negative breast cancer at the RP2D of 150 mg BID. Neither efficacy nor PK were summarized for this study, but the AE profile was consistent with the Phase 1 study. Lastly and importantly, nirogacestat at 150 mg BID was studied in another Phase 2 study conducted by the National Cancer Institute in participants with progressing desmoid tumors ([Kummar et al. 2017](#)). In this study, nirogacestat activity was established with 5 PR (29%) out of 16 evaluable participants. On the basis of the dose-finding Phase I study and the activity in the desmoid tumor Phase 2, the 150 mg BID dose is currently being utilized in the ongoing randomized, double-blinded phase 3 study, Nirogacestat for Adults With Desmoid Tumor/Aggressive Fibromatosis (DT/AF) (DeFi) (ClinicalTrials.gov Identifier: NCT03785964).

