8.4.1.4. Electrolyte Disorder

Selected treatment-emergent abnormally low electrolyte disorder adverse events will be summarized. The electrolyte disorder search definition is a custom MedDRA version 27.0 query based on selected terms from the Metabolism and nutrition disorders and Investigations SOCs. The PTs are as defined below for each electrolyte. The frequency table will be summarized by descending frequency of lab analyte and PT. A shift table will be generated for lab grades in hypocalcemia, hypercalcemia, hypomagnesemia, hypermagnesemia, hypokalemia, hyperkalemia, hyponatremia, and hypernatremia, as well as for clinical categorization in phosphate.

Lab Analyte	Pertinent PTs
Hypocalcemia:	Blood calcium decreased, Hypocalcaemia, Hypocalcaemic seizure
Hypomagnesaemia:	Blood magnesium decreased, Hypomagnesaemia
Hypophosphatemia:	Blood phosphorus decreased, Hypophosphataemia
Hypokalaemia:	Blood potassium decreased, Hypokalaemia, Hypokalaemic syndrome
	Blood sodium decreased, Hyponatraemia, Hyponatraemic coma,
Hyponatremia:	Hyponatraemic encephalopathy, Hyponatraemic seizure, Hyponatraemic syndrome

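### The additional ULN-multiple shift table in SAP 5.6.4 takes the highest post-baseline phosphorus, although the documented concern is low phosphate

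*SAP*

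**What the plan says.** The table is specified in SAP 5.6.4: "Additional shift tables will be produced for ALT, AST, alkaline phosphatase, bilirubin, phosphorus, and creatine showing shifts of below normal range", followed by within normal range and four bands above the ULN (up to 2, 3 and 5 times the ULN, and beyond 5 times), "from baseline to the worst (highest) post baseline value". One rule covers all six tests.

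The same section plans other outputs that include phosphorus. One is general: "Tables for the shift of laboratory data from baseline to the worst post-baseline value will be presented for each lab parameter". Another is by visit: "The shift from baseline to each visit will also be presented for hematology and chemistry parameters". Tests graded in both directions are shown separately for each direction. Tests without a CTCAE grade are shifted to the worst value, high or low, by range indicator. Actual values, changes from baseline, box plots and flagged listings are also planned.

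SAP 8.4.1.4 plans a summary of low-electrolyte adverse events. It also plans shift tables by laboratory grade for calcium, magnesium, potassium and sodium, "as well as for clinical categorization in phosphate". The phosphate categories, and which post-baseline value is used, are not stated there.

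The protocol's phosphate concerns are all on the low side. Section 4.3 lists hypophosphatemia among the important identified risks, Section 6.3 reports it as an adverse event at 150 mg BID in Phase 1, Section 8.3.3.1 says it may require supplementation, Table 7 includes it, and Table 9 makes Grade 3 or higher an adverse event of special interest.

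**The concern.** For ALT, AST, alkaline phosphatase and bilirubin, the highest value is the natural worst case and multiples of the ULN are the natural scale. Phosphorus has been put in the same table with the same rule, so the table calls its highest value the worst. Nothing in either document identifies high phosphate as a risk of nirogacestat.

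The consequence is specific. A participant whose phosphorus falls and later recovers, or is repleted as Protocol 8.3.3.1 anticipates, contributes the recovered value and is counted as within normal range or above. Four of the six categories lie above the ULN and only one lies below normal, with no gradation. A clinical study report reader who goes to this table for phosphorus could conclude that little happened.

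**Working it through.** The documents give no figure to reproduce. The check is one of logic, with an illustration of size.

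**Logic.** Let a participant have k post-baseline values. The maximum is below normal only if all k values are below normal. The minimum is below normal if at least one is. With six values, four low and two normal, the highest-value rule gives within normal range and the lowest-value rule gives below normal. The two rules agree only when no value is low or all are.

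**Inputs.** From the Schedule of Assessments (Protocol 1.3), safety labs are drawn at every visit, so C2 to C7 gives k = 6 and C2 to C13 gives k = 12. The chance p that phosphorus is low at a given visit is not in the documents. It is assumed, over the range 0.10 to 0.80. Correlation between visits within a participant is also assumed, at 0 or 0.5.

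**Formulas.**
- Independent visits: P(all low) = p^k; P(at least one low) = 1 − (1 − p)^k.
- Correlation 0.5: beta-binomial with a = p and b = 1 − p, because (1 − 0.5)/0.5 = 1. P(all low) = B(a + k, b)/B(a, b); P(at least one low) = 1 − B(a, b + k)/B(a, b).

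**Example, k = 6, p = 0.22.** Independent: 0.22^6 = 0.0001 and 1 − 0.78^6 = 0.775. Correlated: P(all low) = (0.22 × 1.22 × 2.22 × 3.22 × 4.22 × 5.22)/720 = 0.059. P(at least one low) = 1 − (0.78 × 1.78 × 2.78 × 3.78 × 4.78 × 5.78)/720 = 0.440.

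**Share of participants shown as below normal, k = 6:**

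| p | Highest, independent | Lowest, independent | Highest, correlation 0.5 | Lowest, correlation 0.5 |
|---|---|---|---|---|
| 0.10 | <0.01% | 47% | 2% | 22% |
| 0.22 | 0.01% | 77% | 6% | 44% |
| 0.50 | 1.6% | 98% | 23% | 77% |
| 0.80 | 26% | >99.9% | 59% | 95% |

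With k = 12 and correlation 0.5, the shares are 3% against 52% at p = 0.22, and 16% against 84% at p = 0.50. Longer follow-up widens the gap, because each extra value is another chance of one normal result. The Schedule of Assessments also draws safety labs at end of treatment and at the 30-day follow-up, which adds further such chances if those values are included.

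**The case against.** The best defence is that low phosphate is well covered elsewhere. SAP 5.6.4 itself plans worst-value shifts for each parameter and by-visit shifts for chemistry. Whether phosphorus is treated as graded or ungraded, either the direction-specific tables or the high-or-low range indicators apply. SAP 5.6.3 gives Hypophosphataemia its own topic, with onset, duration, grade, outcome, dose modification and concomitant medication. SAP 8.4.1.4 adds the low-electrolyte event summary and a separate phosphate shift table. Table shells are held in separate documents (SAP 8.3) and may define what the text leaves open. The study is single-arm with no formal testing, and this is one descriptive table.

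Most of that stands, and it limits the point to this table. Two gaps remain. The text of 8.4.1.4 fixes neither the direction nor the categories for phosphate, so that table is only a partial safeguard. Range indicators show that a value was low but not how low, and event summaries depend on an event having been reported.

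A reader might go further in three ways that the documents do not support:
- That this table cannot show hypophosphatemia at all. It has a below-normal category, which catches participants whose values are all low.
- That the trial would fail to report the toxicity. The outputs above show otherwise.
- That about 12 participants would be misclassified, from 22% of the 53 enrolled (0.22 × 53 = 11.7). The 22% is an adverse-event rate from the Phase 1 solid-tumour study, not a rate of low laboratory values, and it says nothing about how many participants also had a normal value. That count should not be used.

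**Conclusion.** The point holds for one table. As written, the highest-value rule runs in the wrong direction for phosphorus. The table misses intermittent or repleted hypophosphatemia, gives no depth below normal, and captures only participants who are low at every post-baseline assessment. The direction of the error follows from the text alone. Its size rests on the assumed p, k and correlation, and the illustration is not a forecast for this trial; the gap is smaller when low values are persistent within a participant. Hypophosphatemia is one of several important identified risks, and other outputs will report it. No endpoint or efficacy analysis is affected. Severity: minor, a table-specification correction.

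**What to change.** In SAP 5.6.4, do one of the following:
- remove phosphorus from the ULN-multiple, highest-value table; or
- keep it there, with a statement that for phosphorus the lowest post-baseline value is used, with categories graded below the lower limit of normal.

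In SAP 8.4.1.4, state that the phosphate shift runs from baseline to the lowest post-baseline value, and define its categories. If phosphorus leaves the 5.6.4 table, this becomes the one phosphate-specific shift table and nothing is duplicated. Keep the highest value for the other five tests.

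The cost is a sentence in each section and one table shell. No new data are collected.

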## A4-3. LIVER SAFETY: SUGGESTED ACTIONS AND FOLLOW-UP ASSESSMENTS

Liver Chemistry Stopping Criteria	
ALT-absolute	ALT $\geq$ 5 $\times$ ULN
ALT Increase	ALT $\geq$ 3 $\times$ ULN persists for $\geq$ 4 weeks
Bilirubin	ALT $\geq$ 3 $\times$ ULN and total bilirubin $\geq$ 2 $\times$ ULN ( $>$ 35% direct bilirubin)
INR^2	ALT $\geq$ 3 $\times$ ULN and International normalized ratio (INR) $>$ 1.5, if INR measured
Cannot Monitor	ALT $\geq$ 3 $\times$ ULN and cannot be monitored weekly for 4 weeks
Symptomatic	ALT $\geq$ 3 $\times$ ULN associated with symptoms (new or worsening) believed to be related to liver injury or hypersensitivity
Suggested Actions, Follow-up Assessments, and Monitoring	
Actions	

 
Immediately discontinue study treatment (nirogacestat)
 
Report the event to the Sponsor within 24 hours
 
Complete the liver event in the electronic Case Report Form (eCRF) and complete the SAE eCRF form if the event also met the criteria for an SAE
 
Perform liver chemistry follow-up assessments
 
Monitor the participant until liver chemistry test abnormalities resolve, stabilize, or return to baseline (see MONITORING)
 
Restart/rechallenge is not allowed per protocol and not granted, permanently discontinue study treatment and continue participant in the study for any protocol specified follow up assessments
 
	

Follow-Up Assessments	

• Viral hepatitis serology

• Obtain INR and recheck with each liver chemistry assessment until the transaminase values show downward trend

• Serum CPK and LDH

• Fractionate bilirubin, if total bilirubin <math>\geq 2 \times \text{ULN}</math>

• Obtain complete blood count with differential to assess eosinophilia

• Record the appearance or worsening of clinical symptoms of liver injury, or hypersensitivity, on the AE eCRF page

• Record use of concomitant medications (including acetaminophen, herbal remedies, and other over-the-counter medications) on the concomitant medications eCRF page

• Record alcohol use in the eCRF if AE is related to alcohol use

	

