
If <math>\text{ALT} \geq 3 \times \text{ULN}</math> AND <math>\text{bilirubin} \geq 2 \times \text{ULN}</math> or <math>\text{INR} > 1.5</math>:
 

• Repeat liver chemistry tests (include ALT, AST, alkaline phosphatase, bilirubin and INR) and perform liver event follow-up assessments within 24 hours

• Monitor participant twice weekly until liver chemistry test abnormalities resolve, stabilize, or return to baseline

• A specialist or hepatology consultation is recommended

 
If <math>\text{ALT} \geq 3 \times \text{ULN}</math> AND <math>\text{bilirubin} < 2 \times \text{ULN}</math> and <math>\text{INR} \leq 1.5</math>:
 

• Repeat liver chemistry tests (include ALT, AST, alkaline phosphatase, bilirubin and INR) and perform liver chemistry follow-up assessments within 24 to 72 hours

• Monitor participants weekly until liver chemistry abnormalities resolve, stabilize, or return to baseline

 
<math>\text{ALT} \geq 3 \times \text{ULN}</math> and <math>< 5 \times \text{ULN}</math> and <math>\text{bilirubin} < 2 \times \text{ULN}</math>, without symptoms believed to be related to liver injury or hypersensitivity, and who can be monitored weekly for 4 weeks
	

AE = Adverse Event; ALT = Alanine aminotransferase; AST = Aspartate aminotransferase; CPK = Creatine phosphokinase; eCRF = electronic Case Report Form; HPLC = High Performance Liquid Chromatography; IgG = Immunoglobulin G; INR = International normalized ratio; LDH = Lactate dehydrogenase; SAE = Serious Adverse Event; ULN = Upper Limit of Normal;

Serum bilirubin fractionation should be performed if testing is available. If serum bilirubin fractionation is not immediately available, discontinue study treatment if  $\text{ALT} \geq 3 \times \text{ULN}$  and  $\text{bilirubin} \geq 2 \times \text{ULN}$ . Additionally, if serum bilirubin fractionation

testing is unavailable, record the absence/presence of detectable urinary bilirubin on dipstick which is indicative of direct bilirubin elevations suggesting liver injury.

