 All events of ALT  $\geq 3 \times \text{ULN}$  and bilirubin  $\geq 2 \times \text{ULN}$  ( $> 35\%$  direct bilirubin) or ALT  $\geq 3 \times \text{ULN}$  and INR  $> 1.5$  may indicate severe liver injury (**possible 'Hy's Law'**) and must be reported as an SAE (excluding studies of hepatic impairment or cirrhosis). The INR stated threshold value will not apply to participants receiving anticoagulants.

 New or worsening symptoms believed to be related to liver injury (such as fatigue, nausea, vomiting, right upper quadrant pain or tenderness, or jaundice) or hypersensitivity (such as fever, rash or eosinophilia).

 Includes: Hepatitis A immunoglobulin M (IgM) antibody; hepatitis B surface antigen and hepatitis B core antibody; hepatitis C RNA; cytomegalovirus IgM antibody; Epstein-Barr viral capsid antigen IgM antibody (or if unavailable, heterophile antibody or monospot testing); and hepatitis E IgM antibody.

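### The SAP's table of participants meeting the liver stopping criteria does not fully match protocol A4-3, and SAP section 6 does not disclose the differences

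*SAP*

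**What the plan says.** SAP 5.6.4 states: "A summary table and a listing of participants meeting liver chemistry stopping criteria will be provided by the cycle of onset and overall". It then names six conditions, which serve as the definition of the table: ALT ≥5×ULN; ALT ≥3×ULN lasting at least 4 weeks; and ALT ≥3×ULN combined with bilirubin ≥2×ULN (direct fraction above 35%), with INR >1.5 if measured, with weekly monitoring not possible for 4 weeks, or with symptoms. To the monitoring condition the SAP adds a rule of its own: "Missing lab values within window will be considered not monitored".

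Protocol Appendix A4-3 has the same six rows and the same thresholds. Its monitoring text and footnotes qualify them:

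- Monitoring, for ALT ≥3×ULN with bilirubin <2×ULN and INR ≤1.5: "Monitor participants weekly until liver chemistry abnormalities resolve, stabilize, or return to baseline".
- Footnote 1: "If serum bilirubin fractionation is not immediately available, discontinue study treatment if" ALT is ≥3×ULN and bilirubin ≥2×ULN, so no direct fraction is needed in that situation.
- Footnote 2, on the INR condition: "The INR stated threshold value will not apply to participants receiving anticoagulants".
- Symptomatic row: ALT ≥3×ULN "associated with symptoms (new or worsening) believed to be related to liver injury or hypersensitivity". The SAP's version of this row stops at the word 'liver'.

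SAP section 6 lists four changes from the protocol: the PFS-6 definition, the added PFS and OS definitions, the interim assessment that was not done, and added electrolyte preferred terms. None concerns the liver criteria.

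**The concern.** A reader of the study report will take this table as a count of participants who met the protocol's liver criteria. If the programmed conditions differ from A4-3, the count can include people who did not meet them and omit people who did, and nothing in the SAP would warn the reader. Raised transaminases are an important identified risk of the drug (protocol 4.3) and there is no data monitoring committee. The other laboratory summaries in SAP 5.6.4 work one analyte at a time, so they do not reproduce a criterion that combines ALT with bilirubin, INR, monitoring or symptoms.

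**Working it through.** There is no plan figure to reproduce. The check sets the two rule sets side by side and runs one example through each difference. Every example has ALT between 3 and 5×ULN for under 4 weeks and meets no other criterion.

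| Point | Example | A4-3 | SAP 5.6.4 |
|---|---|---|---|
| (a) Monitoring | ALT 3.2×ULN, normal one week later, then not retested | not met: monitoring was possible and ended at resolution | met, if the window is the 4 weeks: the later values are missing |
| (b) INR | INR >1.5 while on an anticoagulant | not met (footnote 2) | met |
| (c) Bilirubin | Bilirubin ≥2×ULN, direct fraction not available | met (footnote 1) | not met as written |
| (d) Symptoms | Hypersensitivity symptoms only | met | not met, if the printed text is complete |

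Points (a) and (b) add participants; (c) and (d) omit them.

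**On (a).** The SAP does not say what the window is. SAP 4.10 sets no visit windows. It also leaves repeat and unscheduled tests out of summary statistics unless otherwise indicated. Weekly liver tests fall between the 28-day visits of year one and the 12-week visits after that, and 5.6.4 does not say that they count here.

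**Do the four points account for all of the disagreement?** Both rule sets were written as logical conditions and compared over every combination of: ALT band (2 levels), bilirubin ≥2×ULN (2), direct fraction above 35%, at or below 35%, or unavailable (3), INR >1.5 (2), anticoagulant (2), persistence ≥4 weeks (2), weekly monitoring done, a value missing, or impossible (3), and symptoms none, liver or hypersensitivity (3). That is 2×2×3×2×2×2×3×3 = 864 profiles. A missing value was taken to mean that monitoring had been possible.

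- Counted by the SAP but not a stopping case under A4-3: 16 profiles. Of these, 8 arise from the missing-value rule alone, 4 from the anticoagulant exception alone and 4 from both (8 + 4 + 4 = 16).
- A stopping case under A4-3 but omitted by the SAP: 12 profiles. Of these, 10 involve hypersensitivity symptoms and would agree once the symptom row is completed. The other 2 come from the bilirubin row (10 + 2 = 12).
- With all four points aligned: 0 discordant profiles.

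These are logical patterns, not expected numbers of participants. They show where the rules part and in which direction, not how often.

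**Size per case.** SAP 5.8 says that 53 participants had been enrolled. If 53 were treated, one misclassified participant moves the percentage by 1/53 = 1.9 points. At the planned 43 it would be 1/43 = 2.3 points.

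**The case against.** **A4-3 may not be the controlling source.** Protocol 9.1.1 points to Figure 2, which is not shown in the text available here, and says that the investigator should consider discontinuation. So the table cannot be read as a list of who should have stopped. That stands. But A4-3 carries its own table headed as the stopping criteria, and the SAP repeats its rows, so whether a criterion was met can still be compared.

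**The bilirubin gap is small.** Footnote 1 is an instruction for the moment when fractionation is not to hand. Direct bilirubin is in the required chemistry panel (protocol Table 14), and A4-3 asks for fractionation once total bilirubin reaches 2×ULN. A fraction still missing at analysis should be rare. A reader might infer that the table hides possible Hy's Law cases. The documents do not support that. Footnote 2 defines those cases by a direct fraction above 35% or by INR, and the SAP captures both. Only an unfractionated case with no qualifying INR could be missed, and footnote 1 makes that a stopping case without making it a Hy's Law case.

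**The symptom row may be lost text.** It breaks off mid-phrase and lacks even the word 'injury'. A reader might infer that hypersensitivity was deliberately dropped, but the text cannot show this.

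**The INR case is narrow.** INR is not a routine test here. Overcounting needs ALT ≥3×ULN, an anticoagulant, a measured INR >1.5 and no other criterion met.

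**The missing-value rule is openly stated and cautious.** It errs toward inclusion. A reader might infer that everyone whose ALT resolves within 4 weeks is counted. That is wrong: those who went on being tested are unaffected.

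**Nothing is hidden.** All laboratory results are listed, with a Grade ≥3 subset; ALT and bilirubin have shift tables in ULN multiples; and AEs and SAEs are listed. This limits the harm, but it does not correct a wrong count in this table.

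**Conclusion.** The concern holds in a limited form. Followed as written, SAP 5.6.4 can misclassify participants in both directions relative to A4-3, and section 6 does not say so. Points (a) and (b) rest on plain text; (a) also depends on how the undefined window is programmed. Point (c) is a real gap that should affect few participants. Point (d) is conditional on checking the SAP file, and the other three do not depend on it. The effect is on one descriptive safety table and its listing, not on efficacy. The number affected cannot be estimated; each participant is 1.9 percentage points, assuming 53 treated. Nothing here judges which clinical stopping rule is right. The point is that the SAP and the protocol must be reconciled.

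**What to change.** Reconcile SAP 5.6.4 with A4-3 and its footnotes:

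- **Monitoring.** Define the window and state that the weekly tests count. Score a missing weekly value as not monitored only if it falls before the first value showing resolution or return to baseline, and say how those are recognised in the data. A4-3 also lets weekly tests end at stabilisation, but neither document defines that in programmable terms, so flag those cases for review.
- **INR.** Flag or exclude participants receiving an anticoagulant at the time.
- **Bilirubin.** Flag and count separately the cases with ALT ≥3×ULN and bilirubin ≥2×ULN but no direct fraction.
- **Symptoms.** Check the SAP file and complete the row to match A4-3.

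Where a departure is intended, keep it and list it in SAP section 6 with the reason.

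The cost is SAP wording, a short definition of resolution and modest programming. ALT, bilirubin, INR where measured, AEs, and concomitant medications with dates and reasons for use are already recorded, so no new data are needed.
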